1.5 Dose Rationale and Risk/Benefits

Safety is our first concern, therefore we have chosen a dose escalation study, starting at a low dose with regular and frequent DSMB safety review. The lowest starting dose in this study is 1 mg weekly, which is expected to achieve <30% 20S proteasome inhibition based on previously published pharmacodynamics data in advanced non-hematologic malignancies (Invest New Drugs. 2015; 33(3): 652–663). The maximum possible dose of ixazomib to be administered in this trial is similar to the doses [name] et al. have previously used in a Phase I study of weekly ixazomib for relapsed/refractory multiple myeloma (60). However, during that study, dosing was BSA based, and the maximum tolerated dose was 2.97 mg/m² (translating to a fixed dose of 5.5 mg). The estimated half-life of ixazomib was 3.6 to 11.3 days, supporting weekly dosing, which is the dosing schedule studied in Phase 2 and 3 trials, and ultimately approved by the FDA for treatment of multiple myeloma.

Furthermore, the doses of ixazomib to be administered in this trial are expected to correlate with the concentrations used in the preliminary data noted above. Maximum biologic effects were noted in the in vitro and ex vivo experiments above with a single treatment of 100 nM ixazomib, which corresponds to a peak in vitro concentration of 36.1 ng/ml. In Study C16009, Arm 3, adult patients with a diagnosis of an advanced non-hematologic malignancy or lymphoma were treated with a standard 4 mg oral dose of ixazomib, and geometric mean C_{max} in the fasted state was 77 ng/ml with a 57% CV. Therefore, the proposed dose range for this study (from 1 to 4 mg) is expected to result in plasma C_{max} values that approximate the doses used in the in vitro studies. C_{min} and C_{max} levels before and after the second dose of ixazomib on Day+15 will be measured.

Potential Risks of ixazomib: Because ixazomib has not been previously studied in HIV infected patients or otherwise healthy individuals, it is unclear what side effects low doses of ixazomib

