5.3 Method for Assigning Subjects to Treatment Groups

Each group (or dose level) will enroll and after 4 weeks of follow up of 3 patients treated with ixazomib at a particular dose will be reviewed for safety by DSMB before initiating enrollment into the next group (or dose level). All patients in the current cohort must have completed 4 weeks and the cohort's data reviewed by the by the Safety Monitoring Committee before patients in the next cohort can receive drug. Patients from the next cohort may complete the first two visits prior to DSMB review of earlier cohorts.

Dose limiting toxicities are defined in Section 6.17 Table 2. After all the subjects in each dosing group has completed Cycle 1 of ixazomib, the DSMB may recommend:

- (i) Proceed to next dose level, or
- (ii) Terminate trial, or
- (iii) Enroll a replacement subject for a withdrawn subject, or
- (iv) Add 5 more patients at previous dose group (maximum tolerated dose). The maximum tolerated dose is that level where no more than 0 out of 3 patients experience dose limiting toxicity.

If no DLT are observed in 3 subjects, the next dosing level will be initiated.

After DSMB review of the 4 mg dosing level, if no DLT are observed, the DSMB may recommend:

- (i) Terminating the trial
- (ii) Enroll 5 more patients at the maximum tolerated dose.

The NNRTIs etravirine and efavirenz are moderate CYP3A enzyme inducers and have potential to decrease systemic exposure to ixazomib. That possibility will be explored by measuring trough ixazomib levels in all patients and comparing ixazomib concentrations in patients on different ART regimens. The DSMB will have to consider the number of patients treated with NNRTIs in a particular group as the safety profile of a group may be underestimated if the majority of patients are treated with NNRTIs as part of their ARV regimen.

Additional data review by the DSMB will occur after Day 84 for each dosing cohort. At this time, the DSMB may recommend:

[figure not shown]
- (i) Proceed to uninterrupted weekly dosing on days 1, 8, 15 and 22 of a 28 day cycle, or
- (ii) Continue previous dosing on days 1, 8, and 15 of a 28 day cycle, or
- (iii) Enroll a replacement subject for a withdrawn subject, or
- (iv) Terminate dosing.

This determination will be made on an individual participant basis, and not a dosing cohort basis, and will be made based on the presence or absence of adverse drug effects that do not meet the definition of dose related toxicities.

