6.15 Visit 15 (Final Study Visit, Time 28 weeks \pm 3 days)

- Obtain vital signs, including weight.
- Monitor for changes to concomitant drug and non-drug treatments.
- Monitor and record adverse events.
- Perform brief physical exam.
- Obtain CBC, CD4 count, HIV RNA viral load, HIV proviral DNA
- Obtain electrolytes, glucose, creatinine, LFTs QLQ-CIPN20 Questionnaire

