6.20 Precautions and Restrictions

Fluid deficit should be corrected before initiation of treatment and during ixazomib treatment. Nonsteroidal anti-inflammatory drugs (NSAIDs) should be avoided with impaired renal function given reported NSAID-induced renal failure in patients with decreased renal function.

The NNRTIs etravirine and efavirenz are moderate CYP3A4 enzyme inducers and have potential to decrease systemic exposure to ixazomib. That possibility will be explored by measuring ixazomib levels in all patients and comparing ixazomib concentrations in patients on different ART regimens.

Pregnancy

It is not known what effects ixazomib has on human pregnancy or development of the embryo or fetus. Therefore, female patients participating in this study should avoid becoming pregnant, and male patients should avoid impregnating a female partner. Male patients should use effective methods of contraception through defined periods during and after study treatment as specified below.

Female patients must meet 1 of the following:

Postmenopausal for at least 1 year before the screening visit, or surgically sterile.

Regardless of above criteria, females must have a negative urine pregnancy test prior to receiving the 1st dose of ixazomib.

Male patients, even if surgically sterilized (ie, status postvasectomy) must agree to 1 of the following:

- Practice effective barrier contraception AND a second method of contraception for female partners of childbearing potential during the entire study treatment period and through 90 days after the last dose of ixazomib, or
- Agree to practice true abstinence, when this is in line with the preferred and usual lifestyle of the subject. (Periodic abstinence [eg, calendar, ovulation, symptothermal, postovulation methods for the female partner] and withdrawal are not acceptable methods of contraception.)
- AND
- Agree to forego sperm donation for the same period as above.

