- life threatening adverse experience
- hospitalization
- inpatient, new, or prolonged; disability/incapacity
- persistent or significant birth defect/anomaly

and/or per protocol may be problems/events that in the opinion of the sponsor-investigator may have adversely affected the rights, safety, or welfare of the subjects or others, or substantially compromised the research data.

All adverse events that do not meet any of the criteria for serious, should be regarded as **non-serious adverse events**.

Adverse Event Reporting Period

For this study, the study treatment follow-up period is defined as 30 days following the last administration of study treatment.

Preexisting Condition

A preexisting condition is one that is present at the start of the study. A preexisting condition should be recorded as an adverse event if the frequency, intensity, or the character of the condition worsens during the study period.

General Physical Examination Findings

At screening, any clinically significant abnormality should be recorded as a preexisting condition. At the end of the study, any new clinically significant findings/abnormalities that meet the definition of an adverse event must also be recorded and documented as an adverse event.

Post-study Adverse Event

All unresolved adverse events should be followed by the sponsor-investigator until the events are resolved, the subject is lost to follow-up, or the adverse event is otherwise explained. At the last scheduled visit, the sponsor-investigator should instruct each subject to report, to the sponsor-investigator, any subsequent event(s) that the subject, or the subject's personal physician, believes might reasonably be related to participation in this study.

Table 3. Adverse Events to be Graded at Each Evaluation

SYSTEM ORGAN CLASS	Adverse event/Symptoms	Baseline	Each evaluation
Investigations	Creatinine increased	X	X
	Neutrophil count decreased	X	X
	Platelet count decreased	X	X
General disorders and administration site conditions	Edema limbs	X	X
	Fatigue	X	X
Gastrointestinal Disorders	Nausea	X	X
	Vomiting	X	X
	# of Stools	X	
	Diarrhea		X
	Constipation		X
Infections and infestations	Sepsis	X	X
Blood and lymphatic system disorders	Febrile neutropenia	X	X
Skin and subcutaneous tissue disorders	Rash, maculopapular	X	X
Nervous system	Peripheral sensory neuropathy	X	X

disorders	Peripheral motor neuropathy	X	X
	Cognitive disturbance	X	X

Hospitalization, Prolonged Hospitalization or Surgery

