8.3.2 Sponsor-Investigator reporting: Notifying the FDA

The sponsor-investigator will report to the FDA all unexpected, serious suspected adverse reactions according to the required IND Safety Reporting timelines, formats and requirements.

Unexpected fatal or life threatening suspected adverse reactions where there is evidence to suggest a causal relationship between the ixazomib and the adverse event, will be reported as a serious suspected adverse reaction. This will be reported to the FDA on FDA Form 3500A, no later than 7 calendar days after the sponsor-investigator's initial receipt of the information about the event.

Other unexpected serious suspected adverse reactions where there is evidence to suggest a causal relationship between the ixazomib and the adverse event, will be reported as a serious suspected adverse reaction. This will be reported to the FDA on FDA Form 3500A, no later than 15 calendar days after the sponsor-investigator's initial receipt of the information about the event.

Any clinically important increase in the rate of serious suspected adverse reactions over those listed in the protocol or product insert will be reported as a serious suspected adverse reaction. This will be reported to the FDA on FDA Form 3500A no later than 15 calendar days after the sponsor-investigator's initial receipt of the information about the event.

Findings from other studies in human or animals that suggest a significant risk in humans exposed to the drug will be reported. This will be reported to the FDA on FDA Form 3500A, no later than 15 calendar days after the sponsor-investigators initial receipt of the information about the event.

AEs which are serious must be reported to Millennium Pharmacovigilance (or designee) from the first dose of ixazomib through 30 days after administration of the last dose of ixazomib. Any SAE that occurs at any time after completion of ixazomib treatment or after the designated follow-up period that the sponsor-investigator and/or sub-investigator considers to be related to ixazomib must be reported to Millennium Pharmacovigilance (or designee). In addition, new primary malignancies that occur during the follow-up periods must be reported, regardless of causality to ixazomib, for a minimum of three years after the last dose of ixazomib, starting from the first dose of ixazomib. All new cases of primary malignancy must be reported to Millennium Pharmacovigilance (or designee).

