8.4 Procedures for Reporting Drug Exposure During Pregnancy and Birth Events

If a woman becomes pregnant or suspects that she is pregnant while participating in this study or within 90 days after the last dose of ixazomib, she must inform the investigator immediately and permanently discontinue ixazomib. The sponsor-investigator must immediately fax a completed Pregnancy Form to the Millennium Department of Pharmacovigilance or designee (see Section 8.2). The pregnancy must be followed for the final pregnancy outcome.

If a female partner of a male patient becomes pregnant during the male patient's participation in this study, the sponsor-investigator must also immediately fax a completed Pregnancy Form to the Millennium Department of Pharmacovigilance or designee (see Section 8.2). Every effort should be made to follow the pregnancy for the final pregnancy outcome.

Suggested Pregnancy Reporting Form:

- Pregnancy Report Form (provided by Millennium)

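### Partner-pregnancy reporting ends with the man's participation, nominally 35 to 42 days after the last dose, although male contraception runs to 90 days; two smaller post-treatment reporting rules also need aligning

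*Combined protocol and SAP*

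**What the plan says.** **Partner pregnancy.** Sections 4.1 and 6.20 require men, even if surgically sterilized, either to practise true abstinence or to use barrier contraception plus a second method "during the entire study treatment period and through 90 days after the last dose of ixazomib". Section 4.2 excludes men unwilling to use a condom for the same 90 days. The partner rule in Section 8.4 begins "If a female partner of a male patient becomes pregnant during the male patient" and is limited to his participation in the study. The preceding paragraph of 8.4 does reach to 90 days after the last dose, but it concerns women who are themselves participants. Sections 4.1 and 6.20 admit women only if they are postmenopausal or surgically sterile.

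**Adverse events.** Under the reporting-period heading of Section 8.1, "the study treatment follow-up period is defined as 30 days following the last administration of study treatment". Section 8.3.2 uses the same 30 days for reporting serious events to the manufacturer; after that, only serious events considered related are reportable. The last scheduled contact is "Visit 15 (Final Study Visit, Time 28 weeks", with a 3-day window either side. Adverse events are collected there (Section 6.15 and Table 1), and Section 8.2 requires recording throughout the study period.

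**Malignancy.** Section 8.3.2 requires new primary malignancies to be reported regardless of causality "for a minimum of three years after the last dose of ixazomib". The instruction given at the last visit (Section 8.1) covers later events that the participant or personal physician "believes might reasonably be related to participation in this study".

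**The concern.** The 90-day contraception rule marks the interval in which the protocol itself treats a pregnancy in a male participant's partner as an exposure of interest. Section 6.20 also says that the drug's effects on human pregnancy and the fetus are not known. Yet the 90-day reporting window is attached to women who, by eligibility, should not become pregnant, and the shorter window to the group in which a pregnancy could occur. A site following Section 8.4 to the letter need not report a partner's pregnancy that begins after Week 28 but inside the 90 days.

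The two secondary points have the same shape. Safety is the primary endpoint, but Section 7.3 gives treatment-emergent reporting no end date. The 30-day period in 8.1 is the only candidate, and it ends before the final visit. For cancers, participants are asked about a narrower set of events than the sponsor-investigator has to report.

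**Working it through.** The documents do not state the interval from last dose to final visit, so there is no plan figure to reproduce. It follows from the calendar.

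**Inputs**
- Six 28-day cycles (Section 5.2). After Day 84 the options in Section 5.3 include "Continue previous dosing on days 1, 8, and 15 of a 28 day cycle" or uninterrupted weekly dosing on days 1, 8, 15 and 22.
- Visit 15 at Week 28, window 3 days either side (Section 6.15).
- Periods after the last dose: 30 days (8.1, 8.3.2), 90 days (6.20), three years (8.3.2).
- Assumption: Visit 3 (Week 0) is study day 1, and all six cycles are given on time.

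**Last dose to Visit 15**
- Cycle 6 day 1 = 5 × 28 + 1 = day 141.
- Last dose = 141 + 14 = day 155 (days 1, 8, 15), or 141 + 21 = day 162 (weekly). Day 155 is also Visit 13 (22 × 7 + 1), where pre-dose and post-dose drug levels are drawn, which supports the dating.
- Visit 15 = 28 × 7 + 1 = day 197.
- Gap = 197 − 155 = 42 days, or 197 − 162 = 35 days.
- If both dose and visit move by 3 days: 36 to 48 days, or 29 to 41 days.

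**Partner pregnancy: part of the 90 days with no reporting requirement**
- Days 1, 8, 15: 90 − 42 = 48 days; 48/90 = 53%.
- Weekly: 90 − 35 = 55 days; 55/90 = 61%.
- With both windows at their extremes: 90 − 48 = 42 days to 90 − 29 = 61 days (47% to 68%).
- The 90 days end on day 155 + 90 = 245 or 162 + 90 = 252, against Visit 15 on day 197.

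This takes participation to end at Visit 15. The summary's 7 months agrees with that if a month is 28 days (7 × 28 = 196 days).

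**Adverse event period against Visit 15**
- 42 − 30 = 12 days, or 35 − 30 = 5 days, between the end of the 30-day period and the nominal visit.
- At the window extremes, 36 − 30 = 6 to 48 − 30 = 18 days, or 29 − 30 = −1 to 41 − 30 = 11 days. A weekly-dosed participant can therefore just fall inside the period.

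**Malignancy.** No arithmetic is needed. The duty is regardless of causality; the instruction is restricted to events believed related. A cancer that the participant thinks unrelated falls under the first and outside the second.

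**The case against.** **On partner pregnancy**, the other side can say that few events are expected: at most 17 participants, with men required to use two methods or abstain. Nothing forbids reporting a later pregnancy, and the consent pages were not available, so they may already ask for it. This stands as a limit on the expected number. It also means that such pregnancies are not required to be reported, rather than that they will go unreported. It does not explain why 8.4 gives the longer window to the group not at risk.

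**On adverse events**, a reader might infer that collection closes at 30 days, so that late neuropathy or CD4 decline is lost. The documents do not support that. Section 6.15, Table 1 and Section 8.2 all require recording at Week 28, and Section 8.1 says that new clinically significant findings at the end of the study that meet the definition must be documented as adverse events. No analysis text applies a 30-day cut. Nor is Visit 15 the only visit off drug: Visit 14 is on day 24 × 7 + 1 = 169, 14 or 7 days after the last dose, prescribes no drug, and collects adverse events, the neuropathy questionnaire, CBC and CD4 count. Possibly related serious events remain reportable without an end date (8.2, 8.3.2).

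A reader might also argue from the statement that "The estimated half-life of ixazomib was 3.6 to 11.3 days" that 30 days is too short. No section sets a required number of half-lives, and across that range 30 days is 30/11.3 = 2.7 to 30/3.6 = 8.3 half-lives. The documents give no basis for a longer period on this ground.

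**On malignancy**, a reader might infer that the three-year duty cannot be met, because 3 × 365 = 1,095 days less 35 to 42 leaves 1,053 to 1,060 days with no scheduled visit. But 8.3.2 states a duty to report, not to search, and a cancer that becomes known can be reported without a visit. The same sentence also refers to follow-up periods that it does not define. What stands is only that the final-visit instruction is narrower than the duty.

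**Conclusion.** The partner-pregnancy point holds and should be corrected. For men who complete all six cycles on schedule, 48 to 55 of the 90 days (53% to 61%) carry no reporting requirement. The size rests on participation ending at Visit 15 and on nominal dates; visit windows move it but do not remove it. For men who stop early the uncovered share depends on when participation is taken to end, which the documents do not tie to the last dose; it could be larger.

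The other two points hold as wording inconsistencies only. The 30-day period and the final visit disagree by a nominal 5 to 12 days. That leaves unclear whether an event first arising in that interval counts as treatment-emergent, and puts serious events not judged related outside the manufacturer's window. The cancer instruction does not match the cancer duty. Neither amounts to lost data collection, and neither calls for added follow-up contacts.

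**What to change.** - **Section 8.4 (main change).** Require a partner's pregnancy to be reported if it occurs during the man's participation or within 90 days after his last dose. Add that instruction for men to Section 6.15 (Visit 15). The contraception rule itself is unchanged.
- **Sections 8.1 and 8.3.2.** End the adverse event reporting period and the manufacturer's serious-event window at Visit 15 or 30 days after the last dose, whichever is later. State in Section 7.3 that Visit 15 findings count in the primary safety tables.
- **Sections 8.1 and 6.15.** At Visit 15, ask participants to report any new cancer whatever they believe its cause, to match 8.3.2.

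The cost is a wording amendment, slightly more reported events among at most 17 people, and matching consent text if the current form does not already cover these points. No visit, call or assessment is added.

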8.2 Recording of Adverse Events

At each contact with the subject, the study team must seek information on adverse events by specific questioning and, as appropriate, by examination. AEs may be spontaneously reported by the patient and/or in response to an open question from study personnel or revealed by observation, physical examination, or other diagnostic procedures. Any clinically relevant deterioration in laboratory assessments or other clinical finding is considered an AE. When possible, signs and symptoms indicating a common underlying pathology should be noted as one comprehensive event. For serious AEs, the investigator must determine both the intensity of the event and the relationship of the event to ixazomib administration.

Information on all adverse events should be recorded immediately in the source document, and also in the appropriate adverse event section of the case report form (CRF). All clearly related signs, symptoms, and abnormal diagnostic, laboratory or procedure results should be recorded in the source document.

All adverse events occurring during the study period must be recorded. The clinical course of each event should be followed until resolution, stabilization, or until it has been ultimately determined that the study treatment or participation is not the probable cause. Serious adverse events that are still ongoing at the end of the study period must be followed up, to determine the final outcome. Any serious adverse event that occurs after the study period and is considered to be at least possibly related to the study treatment or study participation should be recorded and reported immediately.

8.3 Reporting of Serious Adverse Events and Unanticipated Problems

When an adverse event has been identified, the study team will take appropriated action necessary to protect the study participant and then complete the Study Adverse Event Worksheet and log. The sponsor-investigator will evaluate the event and determine the necessary follow-up and reporting required.

8.3.1 Sponsor-Investigator reporting: notifying the Mayo IRB

The sponsor-investigator will report to the Mayo IRB any UPIRTSOs and Non-UPIRTSOs according to the Mayo IRB Policy and Procedures. According to Mayo IRB Policy any serious adverse event (SAE) which the Principal Investigator has determined to be a UPIRTSO must be reported to the Mayo IRB as soon as possible but no later than 5 working days after the investigator first learns of the problem/event.

Information collected on the adverse event worksheet (and entered in the research database) will include:

- Subject's name:
- Medical record number:
- Disease/histology (if applicable):
- The date the adverse event occurred:
- Description of the adverse event:
- Relationship of the adverse event to the research (drug, procedure, or intervention):
- If the adverse event was expected:
- The severity of the adverse event:
- If any intervention was necessary:
- Resolution: (was the incident resolved spontaneously, or after discontinuing treatment)
- Date of Resolution:

The investigator will review all adverse event reports to determine if specific reports need to be made to the IRB and FDA. The sponsor-investigator will sign and date the adverse event report when it is reviewed. For this protocol, only directly related SAEs/UPIRTSOs will be reported to the IRB.

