8.1 Definitions

Unanticipated Problems Involving Risk to Subjects or Others (UPIRTSO)

Any unanticipated problem or adverse event that meets the following three criteria:

- **Serious:** Serious problems or events that results in significant harm, (which may be physical, psychological, financial, social, economic, or legal) or increased risk for the subject or others (including individuals who are not research subjects). These include: (1)

death; (2) life threatening adverse experience; (3) hospitalization - inpatient, new, or prolonged; (4) disability/incapacity - persistent or significant; (5) birth defect/anomaly; (6) breach of confidentiality and (7) other problems, events, or new information (i.e. publications, DSMB reports, interim findings, product labeling change) that in the opinion of the local investigator may adversely affect the rights, safety, or welfare of the subjects or others, or substantially compromise the research data, **AND**

- **Unanticipated:** (i.e. unexpected) problems or events are those that are not already described as potential risks in the protocol, consent document, not listed in the Investigator's Brochure, or not part of an underlying disease. A problem or event is "unanticipated" when it was unforeseeable at the time of its occurrence. A problem or event is "unanticipated" when it occurs at an increased frequency or at an increased severity than expected, **AND**
- **Related:** A problem or event is "related" if it is possibly related to the research procedures.

Adverse Event

An untoward or undesirable experience associated with the use of a medical product (i.e. drug, device, biologic) in a patient or research subject. An AE can therefore be any unfavorable and unintended sign (including an abnormal laboratory finding), symptom, or disease temporally associated with the use of a medicinal (investigational) product whether or not it is related to the medicinal product. This includes any newly occurring event, or a previous condition that has increased in severity or frequency since the administration of ixazomib.

An abnormal laboratory value will not be assessed as an AE unless that value leads to discontinuation or delay in treatment, dose modification, therapeutic intervention, or is considered by the investigator to be a clinically significant change from baseline.

Serious Adverse Event

Adverse events are classified as serious or non-serious. Serious problems/events can be well defined and include;

- death

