In the event that this is a multisite study, the sponsor-investigator is responsible to ensure that the SAE reports are sent to Millennium Pharmacovigilance (or designee) from all sites participating in the study. Sub-investigators must report all SAEs to the sponsor-investigator so that the sponsor-investigator can meet his/her foregoing reporting obligations to the required regulatory agencies and to Millennium Pharmacovigilance, unless otherwise agreed between the sponsor-investigator and sub-investigator(s).

Relationship to ixazomib for each SAE will be determined by the investigator or sub-investigator by responding yes or no to the question: Is there a reasonable possibility that the AE is associated with the ixazomib?

Sponsor-investigator must also provide Millennium Pharmacovigilance with a copy of all communications with applicable regulatory authorities related to ixazomib as soon as possible but no later than 4 calendar days of such communication.

SAE and Pregnancy Reporting Contact Information

US & Canada

[contact]

Email: [contact]

Rest of World

[contact]

E-mail: [contact] Suggested Reporting Form:

- SAE Report Form (provided by Millennium)
- US FDA MedWatch 3500A:
<http://www.fda.gov/Safety/MedWatch/HowToReport/DownloadForms/default.htm>
- Any other form deemed appropriate by the sponsor-investigator

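### The last sentence of Section 8.3.1 limits IRB reporting to directly related events, contradicting the possibly-related threshold in 8.1 and the opening of 8.3.1

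*Combined protocol and SAP*

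**What the plan says.** Section 8.1 defines a UPIRTSO as "Any unanticipated problem or adverse event that meets the following three criteria". The three are serious, unanticipated and related, joined by AND. For the third, an event counts as related "if it is possibly related to the research procedures".

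Section 8.3.1 begins: "The sponsor-investigator will report to the Mayo IRB any UPIRTSOs and Non-UPIRTSOs according to the Mayo IRB Policy and Procedures". It adds that a serious adverse event (SAE), once judged by the principal investigator to meet that definition, "must be reported to the Mayo IRB as soon as possible but no later than 5 working days", counted from when the investigator learns of it. Neither statement sets a higher threshold of relatedness.

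The section closes: "For this protocol, only directly related SAEs/UPIRTSOs will be reported to the IRB".

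Two other places set a threshold for causality. Section 8.2 says of SAEs arising once the study has ended that any "considered to be at least possibly related to the study treatment or study participation should be recorded and reported immediately"; it does not name the recipient. Section 8.3.2 has the investigator answer yes or no, for each SAE, to the question "Is there a reasonable possibility that the AE is associated with the ixazomib".

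**The concern.** The closing sentence is worded as a limit specific to this protocol, so site staff could reasonably take it as the rule to follow. It sets a stricter test than the definition it is applied to, and the test is undefined. Two investigators could classify the same event differently, and a monitor would have no standard against which to check either of them.

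The IRB's view of unexpected harm is at stake. Section 1.4 says there is no published experience with ixazomib in HIV-positive persons, and 1.5 allows that toxicities not seen before may occur. With at most 17 participants (4.3), a single unexpected serious event could be a large share of the safety information, and its cause may be uncertain when it is first reported.

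**Working it through.** No arithmetic applies: the point depends on no rate, sample size or error level. The check is to take each type of event through the two rules in 8.3.1.

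1. **Serious, unanticipated, directly related.** It meets all three criteria in 8.1. The opening paragraph requires a report and the last sentence allows one. There is no conflict.

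2. **Serious, unanticipated, possibly but not directly related.** It also meets all three criteria, because possible relatedness satisfies the third. The opening paragraph requires a report, within 5 working days if it is an SAE so judged. The last sentence excludes it. Both cannot be followed.

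3. **Serious but anticipated.** It fails the second criterion, so it is not a UPIRTSO. The opening sentence leaves it to IRB policy, which is not among the documents. The last sentence would admit it if directly related and exclude it otherwise. Whether the two rules agree cannot be settled here.

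4. **Serious and unrelated.** It is not a UPIRTSO. The opening sentence again defers to IRB policy, and the last sentence excludes it. Whether they agree cannot be settled here either.

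The demonstrable contradiction is case 2.

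The next step is to see where a case 2 event would still go if the last sentence were applied:

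- **Supplier's pharmacovigilance (8.3.2):** every SAE, whatever its causality or expectedness.
- **FDA (8.3.2):** "The sponsor-investigator will report to the FDA all unexpected, serious suspected adverse reactions". The causality wording there concerns ixazomib, whereas 8.1 refers to research procedures, which include the two leukaphereses in Table 1.
- **Monitoring committee (9.3):** death, anaphylaxis, life-threatening events, any Grade 4 event, any Grade 3 event not clearly unrelated to study drug, and two laboratory triggers (CD4 count and virologic rebound). The principal investigators report the resulting action to the IRB and FDA on the timelines of 8.3.1 and 8.3.2.
- **IRB, by general duty (8.3.2):** the principal investigator is responsible for reporting SAEs to the IRB. No relatedness threshold is stated.

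The 9.3 list does not cover everything that 8.1 calls serious. For example, a hospitalization for an event below Grade 3 is serious under 8.1 but is not a 9.3 trigger. Such an event, if unanticipated and possibly related, depends on 8.3.1 and the general duty in 8.3.2 to reach the IRB.

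**The case against.** The strongest reply is that safety reporting does not rest on this sentence alone. The supplier, FDA and committee routes all operate without a test of direct relatedness, and 9.3 provides a partial further route to the IRB. This stands, and it limits the point to IRB notification. A reader might infer that possibly related serious events would go unreported altogether; 8.3.2 and 9.3 rule that out. But these routes do not replace the report that the opening of 8.3.1 itself requires, and what 9.3 means by the action to be reported is open to interpretation.

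A second reply is that the opening sentence cites IRB policy, which may prevail over a protocol sentence. It may, but the policy is not in the documents and staff should not have to guess. For the same reason it would be too strong to say that the last sentence overrides the first. The text shows that they are inconsistent.

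A third reply is that the authors meant only to leave out unrelated SAEs. That is possible, but the qualifier goes further, and it is attached to UPIRTSOs, which are related by definition.

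Three further inferences are tempting and lack support:

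- **Most serious events here would be only possibly related.** Section 1.5 does call attribution difficult, but it is explaining earlier trials, whose participants had underlying disease and overlapping therapies. No rate is given for this population.
- **No recorded category could match direct relatedness.** The yes/no question in 8.3.2 has none, but the worksheet in 8.3.1 has its own relationship field, and its response options are not stated.
- **The open-label design makes the last sentence worse.** The opening rule also relies on the principal investigator's judgement, so this does not separate the two.

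**Conclusion.** The contradiction is real and is in the current text. For a serious, unanticipated event judged possibly but not directly related, the opening and closing of 8.3.1 give opposite instructions. If the closing sentence is followed, such events might not be reported to the IRB under that section. How often this would happen cannot be estimated from the documents.

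The conclusion assumes that direct relatedness is meant as a stricter test than possible relatedness. That is the natural reading of the words, but the protocol does not say so. The problem is an internal inconsistency in an operative safety instruction. It affects no endpoint, dose-escalation decision or analysis, but should be corrected because it concerns oversight of unexpected harm.

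**What to change.** Delete the last sentence of 8.3.1. The definition in 8.1 and the opening paragraph of 8.3.1, with its 5-working-day limit, then govern without contradiction.

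Substituting possible for direct relatedness within that sentence would not be enough. The word 'only' would remain and would still conflict with the opening sentence, which also covers Non-UPIRTSOs. The sentence would also take in anticipated SAEs, which are not UPIRTSOs under 8.1.

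The change is one sentence. Its downside is possibly a few more reports to the IRB.
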